6.1.1. End of Study Definition

The end of study is defined as the last visit of the last patient.

6.1.2. Study Design Safety Considerations**The design considers important safety issues:**

- All DBPCFC visits will be supervised in-clinic setting where trained study physicians are available
- Standing orders from a medical doctor are provided for all clinical study personnel to initiate treatment of reactions immediately (ie, prior to medical doctor notification), including IM administration of epinephrine, based on their own clinical judgment
- A crash cart with pediatric equipment will be available in close proximity (within 50 feet) of all patient clinic rooms
- A code team is available
- Dosing allergic symptoms and AEs will be captured throughout the study
- Patients will be prescribed an epinephrine auto-injector (if not prescribed by a treating clinician previous to study entry) and all patients/Caregivers will be trained in its use. Patients will be advised to carry the autoinjector with them at all times.
- Patients /caregivers will be cautioned against patients consuming any peanuts or peanut-containing foods other than the peanut allergen challenge while on study
- The dupilumab clinical development program in food allergy independent data monitoring committee (IDMC) will provide oversight of patient safety. The IDMC will provide Regeneron and Sanofi with appropriate recommendations on the conduct of the food allergy clinical studies to ensure the protection and safety of the patients enrolled in these studies.

6.1.3. Study Stopping Rules

6.1.3.1. Individual Patient Stopping Rules (both study drug and food challenge)

1. Missing ≥ 2 consecutive doses of study drug
2. Anaphylaxis resulting in severe hypotension ([Appendix 3](#)), neurological compromise or mechanical ventilation secondary to any food challenge ([Simons, 2014](#)).
3. Patient develops biopsy-documented eosinophilic esophagitis (EoE) or other eosinophilic gastrointestinal disease.
4. Any patient deemed to have severe allergic reactions and who receives aggressive therapy (eg, mechanical ventilation, 3 or more repeated doses of epinephrine for a life-threatening reaction) at any time will be discontinued from further therapy.
5. Other circumstances including, but not limited to, the following:
 - Poor control or persistent severe activation of secondary atopic disease (eg, AD, asthma)
 - Started on beta-blockers with no alternative medications available per the prescribing physician
 - Pregnancy

6.1.3.2. Anaphylaxis

The definition of anaphylaxis that has been adopted for this study is from the 2014 position paper by the European Academy of Allergy and Clinical Immunology (EAACI) Food Allergy and Anaphylaxis Guidelines Group ([Muraro, 2007](#)), that in turn was based on the publications of Simons ([Simons, 2011](#)) and Johansson ([Johansson, 2004](#)), and is consistent with the recently published “International consensus on (ICON) anaphylaxis” ([Simons, 2014](#)). Accordingly, anaphylaxis is defined as a severe, potentially life-threatening systemic hypersensitivity reaction, characterized by being rapid in onset with life-threatening airway, breathing, or circulatory problems that is usually, though not always, associated with skin and mucosal changes.

When the diagnosis of anaphylaxis is made, the basis for having suspected the diagnosis must be documented, using the criteria established by the Second Symposium on the Definition and Management of Anaphylaxis ([Sampson, 2006](#)). Reports of anaphylaxis will be collected in the electronic data capture (EDC). Reports of non-fatal and non-life-threatening anaphylaxis that do not require hospitalization (admitted for over 24 hours) will not require expedited safety reporting, as these are clinically anticipated events in the target population. All reports of anaphylaxis will be periodically reviewed to ensure proper patient care and prompt identification of any clinically concerning safety issues.

6.2. Planned Interim Analysis

No formal interim analysis is planned for this study.

Data may be analyzed and reviewed internally by the sponsors.

A primary analysis may be performed once all patients in the study have completed the 24-week treatment period as specified in the protocol (week 24 visit or earlier for those patients who are withdrawn prematurely from the study). If performed, this primary analysis will be considered the final analysis for the primary endpoint and secondary efficacy endpoints up to week 24. A description of the statistical methods to be employed is in Section 11.4.

6.3. Study Committees

6.3.1. Independent Data Monitoring Committee

The dupilumab clinical development program in food allergy IDMC, composed of members who are independent from the sponsor and the study investigators, will provide oversight of patient safety by conducting formal reviews of accumulated safety data. The IDMC will provide Regeneron and Sanofi with appropriate recommendations on the conduct of the food allergy clinical studies to ensure the protection and safety of the patients enrolled in these studies.

All activities and responsibilities of the IDMC are described in the IDMC charter.

7. SELECTION, WITHDRAWAL, AND REPLACEMENT OF PATIENTS

7.1. Number of Patients Planned

Approximately 24 patients with a history of confirmed peanut allergy will be enrolled at approximately 10 sites in the US and Canada (CAN).

7.2. Study Population

Male and female pediatric patients ages 6 to 17 years inclusive with a history of peanut allergy confirmed by peanut SPT, sIgE, and by the amount of peanut protein (mg) safely ingested during a peanut DBPCFC.

7.2.1. Inclusion Criteria

A patient must meet the following criteria to be eligible for inclusion in the study:

1. Age 6 to 17 years (inclusive).
2. Patient has a clinical history of allergy to peanuts or peanut-containing foods (symptom[s] of reaction due to exposure).
3. Experience dose-limiting symptoms at or before the 100 mg challenge dose (≤ 144 mg cumulative) of peanut protein (measured as 200 mg of peanut flour) on screening DBPCFC conducted in accordance with PRACTALL (Practical Issues in Allergology, Joint United States/European Union Initiative) guidelines. And not experiencing dose limiting symptoms to placebo
4. Serum IgE to peanut of ≥ 10 kUA/L and/or a SPT to peanut ≥ 8 mm compared to a negative control.

5. Patients/legal guardians must be trained on the proper use of the epinephrine autoinjector device to be allowed to enroll in the study.
6. Patients with other known food allergies must agree to eliminate these other food items from their diet so as not to confound the safety and efficacy data from the study.
7. Written informed consent from parent/guardian.
8. Written assent from minor patients as appropriate (eg, above the age of 6 years or the applicable age per local regulatory requirements).
9. Willing and able to comply with all clinic visits and study-related procedures.

7.2.2. Exclusion Criteria

A patient who meets any of the following criteria will be excluded from the study:

1. Any previous exposure to marketed dupilumab or dupilumab in a clinical trial
2. Member of the clinical site study team or his/her immediate family
3. History of other chronic disease (other than asthma, AD, or allergic rhinitis) requiring therapy (eg, heart disease, diabetes, hypertension) that, in the opinion of the Principal Investigator, would represent a risk to the patient's health or safety in this study or the patient's ability to comply with the study protocol
4. History of frequent or recent severe, life-threatening episode of anaphylaxis or anaphylactic shock as defined by more than 3 episodes of anaphylaxis within the past year and/or an episode of anaphylaxis within 60 days of screening DBPCFC
5. History of eosinophilic gastrointestinal disease
6. History of eosinophilic granulomatosis with polyangiitis
7. Current participation or participation within 6 months prior to screening in any other interventional study.
8. Severe, unstable asthma at time of enrollment or any patient with FEV1 <80% of predicted or ACQ >1.5.
9. Use of systemic corticosteroids within 2 months prior to screening
10. Use of omalizumab, benralizumab, or mepolizumab within 6 months prior to screening.
11. Use of other forms of allergen immunotherapy (eg, oral, SC, patch or sublingual) or immunomodulatory therapy (not including corticosteroids) within 3 months prior to screening.
12. Use of antihistamines within 5 days prior to screening and within 5 days prior to SPTs and day 1 of DBPCFCs.
13. Use of any agents known or likely to interact with epinephrine (eg, beta blockers, ACE-inhibitors, tri-cyclic antidepressants, or other drugs), within 3 weeks prior to screening.
14. Allergy to oat (placebo in DBPCFC).
15. Hypersensitivity to epinephrine and any of the excipients in the epinephrine product.

16. History of a mast cell disorder, including mastocytosis, urticarial pigmentosa, and hereditary or idiopathic angioedema.
17. Treatment with a live (attenuated) vaccine within 3 months before the baseline visit and during the study
18. Active chronic or acute infection requiring systemic treatment with antibiotics, antivirals, antiparasitics, antiprotozoals, or antifungals within 2 weeks prior to the baseline visit.
NOTE: patients may be rescreened after the infection resolves.
19. History of malignancy within 5 years before the screening visit, except completely treated in situ carcinoma of the cervix, completely treated and resolved non-metastatic squamous or basal cell carcinoma of the skin.
20. Established diagnosis of a primary immunodeficiency disorder (eg, Severe Combined Immunodeficiency, Wiskott Aldrich Syndrome, DiGeorge Syndrome, X-linked Agammaglobulinemia, Common Variable Immunodeficiency), or secondary immunodeficiency.
21. Known history of human immunodeficiency virus (HIV) infection or HIV seropositivity at the screening visit.
22. With an established diagnosis of hepatitis B viral infection at the time of screening or is positive for hepatitis surface antigen (HBsAg) or hepatitis core antibody (HBcAb) at the time of screening
23. Body weight <20 kg
24. Pregnant or breastfeeding women, women planning to become pregnant or breastfeed during the study.
25. Girls at or beyond menarche who are not sexually abstinent and are unwilling to practice highly effective contraception prior to the initial dose/start of the first treatment, during the study, and for at least 12 weeks after the last dose. Highly effective contraceptive measures include stable use of combined (estrogen and progestogen containing) hormonal contraception (oral, intravaginal, transdermal) or progestogen-only hormonal contraception (oral, injectable, implantable) associated with inhibition of ovulation initiated 2 or more menstrual cycles prior to screening; intrauterine device (IUD); intrauterine hormone releasing system (IUS); bilateral tubal ligation; vasectomized partner; and or sexual abstinence.

†Sexual abstinence is considered a highly effective method only if defined as refraining from heterosexual intercourse during the entire period of risk associated with the study treatments. The reliability of sexual abstinence needs to be evaluated in relation to the duration of the clinical trial and the preferred and usual lifestyle of the patient.

‡Periodic abstinence (calendar, symptothermal, post-ovulation methods), withdrawal (coitus interruptus), spermicides only, and lactational amenorrhoea method (LAM) are not acceptable methods of contraception. Female condom and male condom should not be used together.

7.3. Premature Withdrawal from the Study

A patient has the right to withdraw from the study at any time, for any reason, and without repercussion.

The investigator and/or sponsor have the right to withdraw a patient from the study if it is no longer in the interest of the patient to continue in the study, or if the patient's continuation in the study places the scientific outcome of the study at risk (eg, if a patient does not or cannot follow study procedures). An excessive rate of withdrawals would render the study uninterpretable; therefore, unnecessary withdrawal of patients should be avoided.

Patients who are withdrawn prematurely from the study will be asked to complete study assessments, as described in Section 9.1.2.

Rules for discontinuation of study treatment (permanent or temporary) are discussed in Section 8.3.2.

7.4. Replacement of Patients

Patients prematurely discontinued from study will not be replaced.

8. STUDY TREATMENTS

8.1. Investigational and Reference Treatments

Dupilumab 175 mg/mL (200mg dose): Each single-use, prefilled syringe delivers 200 mg of study drug (1.14 mL of a 175 mg/mL solution, expellable in 1mL syringe).

Dupilumab 150 mg/mL (300mg dose): Each single-use, prefilled syringe delivers 300 mg of study drug (2.0 mL of a 150 mg/mL solution, expellable in 2.25mL syringe).

Subcutaneous injection sites of the study drug should be alternated among the different quadrants of the abdomen (avoiding navel and waist areas), upper thighs, and upper arms so that the same site is not injected for 2 consecutive administrations.

Instructions on dose preparation are provided in the pharmacy manual.

8.1.1. Peanut for Double-Blind Placebo-Controlled Food Challenge

For the DBPCFC, peanut flour or placebo food challenge mixture will be administered in a food vehicle. Investigational sites will be provided with standardized recipes for preparation of the DBPCFC in a separate manual of procedures.

8.2. Rescue Treatments

If required, patients who experience allergic reactions will be treated with IM or SC administration of epinephrine at the discretion of the clinical study personnel based on their own clinical judgement. The clinical site will also collect rescue medications taken at home in the event of accidental exposure to peanut. For more details, see Section 6.1.2.

8.3. Dose Modification and Study Treatment Discontinuation Rules

8.3.1. Dose Modification

Dose modification for an individual patient is not allowed.

8.3.2. Study Drug Discontinuation

Patients who permanently discontinue from study drug and who do not withdraw from the study will be asked to return to the clinic for all remaining study visits per the visit schedule.

Patients who permanently discontinue from study drug and who opt to withdraw from the study will be asked to complete study assessments, per Section 9.1.2.

8.3.2.1. Reasons for Permanent Discontinuation of Dupilumab and Food Challenge

Study drug dosing will be permanently stopped in the event of:

- Anaphylactic reaction or other severe systemic reaction to dupilumab
- Any infection that is opportunistic, such as active tuberculosis and other infections whose nature or course may suggest an immuno-compromised status
- Severe laboratory abnormalities that are deemed to be related to dupilumab:
 - Neutrophil count $\leq 0.5 \times 10^3/\mu\text{L}$
 - Platelet count $\leq 50 \times 10^3/\mu\text{L}$
 - ALT and/or AST values greater than $3 \times \text{ULN}$ with total bilirubin $>2 \times \text{ULN}$ (unless elevated bilirubin is related to confirmed Gilbert's Syndrome)
 - Confirmed AST and/or ALT $>5 \times \text{ULN}$ (for more than 2 weeks)
- Diagnosis of a malignancy during the study
- Evidence of pregnancy
- Treatment with any prohibited concomitant medication or procedure
- Missing ≥ 2 consecutive doses of study drug (dupilumab)

8.3.2.2. Reasons for Temporary Discontinuation of Dupilumab

Study drug dosing will be temporarily discontinued in the event of:

- Clinically important laboratory abnormalities such as:
 - ALT or AST $3 \times \text{ULN}$ but $\leq 5 \times \text{ULN}$
 - CPK $>2.5 \times \text{ULN}$
 - Serum creatinine $>1.5 \times \text{ULN}$

- Severe laboratory abnormalities (as noted in Section 8.3.2.1) where a causal relationship to dupilumab can be reasonably excluded (ie, an alternative cause is evident). In these cases, study treatment will be discontinued while the clinical circumstances are being assessed but it may be resumed when the laboratory parameters normalize sufficiently. A decision to resume treatment will be made jointly by the investigator and medical monitor.
- Other intercurrent illnesses or major surgery
- An infection that requires parenteral treatment with antibiotic, antifungal, antiviral, antiparasitic, or antiprotozoal agents, or requires oral treatment with such agents for longer than 2 weeks.

After the condition leading to suspension of dosing normalizes sufficiently, study treatment may resume at the discretion of the principal investigator in consultation with the medical monitor. A decision to discontinue study drug and/or to reinstitute study treatment should be discussed with the medical monitor. Note that dosing may NOT be resumed if patient met conditions for permanently discontinuing study drug described in Section 7.3 . The investigator may suspend study treatment at any time, even without consultation with the medical monitor, if the urgency of the situation requires immediate action and if this is determined to be in the patient's best interest. However, the medical monitor should be contacted as soon as possible in any case of study drug discontinuation. Resumption of study treatment after temporary discontinuation should always be discussed with the medical monitor.

8.4. Management of Acute Reactions

8.4.1. Acute Injection Reactions

8.4.1.1. Systemic Injection Reactions

Acute systemic reactions following injection of study drug (SC) should be treated using clinical judgment to determine the appropriate response according to typical clinical practice.

8.4.1.2. Local Injection Site Reactions

Local injection site reactions must be reported as AEs and graded according to the Food and Drug Administration (FDA) September 2007 Guidance for Industry, Toxicity Grading Scale for Healthy Adult and Adolescent Volunteers Enrolled in Preventive Vaccine Clinical Trials (provided in the study Regulatory Binder, also see Section 10.5.1).

8.5. Method of Treatment Assignment

Approximately 24 patients will be enrolled using an interactive web response system (IWRS).

8.5.1. Blinding

This is an open-label study.

For the DBPCFC, an unblinded pharmacist or designee will mix the peanut protein or oat protein in a chocolate food matrix that masks taste for administration in the DBPCFC. For each patient, a “blinded” evaluating physician (Blinded Assessor) is to be designated to assess the tolerability of the challenge doses presented in the DBPCFC. The blinded evaluating physician is not to be involved directly in the oversight of study product dosing or the assessment or management of AEs (for details refer to the Masking Plan). To the extent practicable, the same blinded evaluating physician who determines dose limiting symptoms (DLS) in the screening DBPCFC should determine DLS in the week 24 and 36 DBPCFCs.

8.6. Treatment Logistics and Accountability

8.6.1. Packaging, Labeling, and Storage

Study drug for injection will be provided as open-label kits. Each carton box will contain 1 labeled prefilled syringe. The carton box and prefilled syringe label will indicate the protocol number, product identity and strength, medication/reference number, batch number, directions for use, route of administration, expiry date, sponsor information, and storage conditions, and will correspond to all regulatory requirements.

Study drug will be stored at the site at a temperature of 2°C to 8°C; storage instructions will be provided in the pharmacy manual.

8.6.2. Supply and Disposition of Treatments

Study drug will be shipped at a temperature of 2°C to 8°C to the investigator or designee at regular intervals or as needed during the study. At specified time points during the study (eg, interim site monitoring visits), at the site close-out visit, and following drug reconciliation and documentation by the site monitor, all opened and unopened study drug will be destroyed on site after approval from sponsor or designee, or returned to a destruction depot after accountability and reconciliation.

8.6.3. Treatment Accountability

All drug accountability records must be kept current.

The investigator must be able to account for all opened and unopened study drug. These records should contain the dates, quantity, and study medication

- dispensed to each patient,
- returned from each patient (if applicable), and
- disposed of at the site or returned to the sponsor or designee.

All accountability records must be made available for inspection by the sponsor and regulatory agency inspectors; photocopies must be provided to the sponsor at the conclusion of the study.

8.6.4. Treatment Compliance

All drug compliance records must be kept current and made available for inspection by the sponsor and regulatory agency inspectors.

8.7. Concomitant Medications and Procedures

Any treatment administered from the time of the first dose of study drug to the final study visit will be considered concomitant medication. This includes medications that were started before the study and are ongoing during the study.

The use of prohibited medications should only be considered when necessary for the patient's care and well-being and when there are no other options. Their use results in permanent treatment discontinuation but not discontinuation from study.

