4.1.2. Secondary Endpoints

- Change in the cumulative tolerated dose (log transformed) mg of peanut protein during a DBPCFC from baseline to measured DBPCFC visits at weeks 24 and 36.
- Proportion of patients treated with dupilumab that pass a DBPCFC with at least 444 mg (cumulative) peanut protein at week 36.
- Proportion of patients treated with dupilumab that pass a DBPCFC with at least 1044 mg (cumulative) peanut protein at weeks 24 and 36.
- Proportion of patients treated with dupilumab that pass a DBPCFC with 2044 mg (cumulative) peanut protein at weeks 24 and 36.
- Percent change from baseline in sIgE to post-baseline visits (weeks 4, 8, 12, 24, and 36)
- Change from baseline in titrated SPT at week 4, 12, 24, 36 as measured by the average wheal size AUC after peanut allergen stimulation at different concentrations.
- Proportion of patients with Grade II or above allergic reactions during the DBPCFC at week 24
- Proportion of patients using epinephrine as a rescue medication during the DBPCFC at week 24

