Double-Blind Placebo-Controlled Food Challenge

At week 24, under intensive monitoring, all patients will undergo a DBPCFC up to 2044 mg peanut protein (cumulative) or placebo (see [Appendix 1](#)) to assess tolerability. The patient's sensitivity to peanut allergen is defined as the dose at which the patient experiences allergic reactions. All symptoms and signs will be evaluated and rated based on a standardized oral food challenge scoring system (see [Appendix 2](#)). Up-dosing during the DBPCFC will be stopped when the blinded assessor finds symptoms and/or signs that indicate a definite objective allergic reaction (CoFAR grading system [see [Appendix 2](#)]) has occurred based on clinically significant changes in reported symptoms, physical findings, or vital signs that the patient is experiencing to the challenge material. Vital signs will be assessed every 15 to 30 minutes. The DBPCFC will consist of 8 doses (peanut protein or placebo), with a dose given every 15 to 30 minutes: 1, 3, 10, 30, 100, 300, 600 mg, and 1000 mg resulting in a total challenge of up to 2044 mg peanut protein (cumulative). Both peanut and oat protein will be concealed in a food that masks the taste. The food challenges will be performed on different days (1 day placebo [oat] protein, 1 day peanut protein, with order determined at random) at least 24 hours but not more than 7 days apart and not within 24 hours of a dose of study drug. Patients will be considered to have passed the DBPCFC if they do not experience any objective Grade 1 reaction by the CoFAR grading system (see [Appendix 2](#)). If the patient experiences reactions, he/she will be treated with the necessary rescue medications. He/she will be observed for a minimum of 2 hours after the final administered dose and discharged only when deemed clinically stable by a study physician. Symptom severity will be adjudicated by an independent, blinded assessor who is not involved in patient study visit conduct ([Bock, 1988](#); [Sampson, 2006](#)).

Study design safety considerations for DBPCFC are described in Section [3.3.2](#).

Post-Treatment Follow-up Period (12 weeks)

All patients will have a 12-week follow-up period after the end of treatment and will undergo safety, laboratory, and clinical assessments.

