8.7.1. Prohibited Medications and Procedures

Treatment with the following concomitant medications is prohibited during the study:

- Treatment with a live (attenuated) vaccine; below is a list of examples of such vaccines. Refer to study manual for a current, comprehensive list of prohibited vaccines

Chickenpox (Varicella)	Oral typhoid
FluMist-Influenza	Rubella
Intranasal influenza	Smallpox (Vaccinia)
Measles (Rubeola)	Yellow fever
Measles-mumps-rubella combination	Bacillus Calmette-Guerin
Measles-mumps-rubella-varicella combination	Rotavirus
Mumps	Varicella Zoster (shingles)
Oral polio (Sabin)	

- Treatment with an investigational drug (other than dupilumab)
- Treatment with immunomodulating biologic agents, including anti-IgE
- Treatment with allergen immunotherapy
- Treatment with systemic (oral, IV, IM, SC) corticosteroids for a duration of more than 5 continuous days, more than 15 days in total, or within 2 days prior to DBPCFCs
- Treatment with any agents known or likely to interact with epinephrine (eg, beta blockers, ACE-inhibitors, tri-cyclic antidepressants, or other drugs)
- Treatment with antihistamines within 5 days prior to screening and within 5 days prior to SPTs and day 1 of DBPCFCs

The following concomitant procedures are prohibited during study participation:

- Major elective surgical procedures

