9.1.1. Footnotes for the Schedule of Events Table

1. Study drug will be administered in the clinic on day 1 by the study team, patient's caregiver, or patient. With adequate training, study drug may be administered at home Q2W for the remaining injections. Patient/caregiver will complete an injection log to document compliance with injection of study drug and to document any AEs and concomitant medications.
2. During DBPCFC, vital signs will be collected every 15 to 30 minutes. After initial DBPCFC dose, only pulse and blood pressure need to be taken as part of safety monitoring.
3. Patients should not take antihistamines within 5 days prior to SPTs and day 1 of the DBPCFCs.
4. The food challenges (DBPCFC) will be performed on different days (1 day placebo [oat] protein, 1 day peanut protein, with order determined at random) at least 24 hours, but no more than 7 days, apart and not within 24 hours of a dose of study drug. After the last dose of the DBPCFC, the patient will be monitored for at least 2 hours and then discharged from the clinic.
5. Assessments will be performed before the administration of study drug.
6. FeNO measurement and spirometry will be performed on the same day, except for visit 1, in which only spirometry is performed. If the DBPCFC is scheduled on the day of the visit, then both FeNO measurement and spirometry will be performed twice before the patient goes home: once before DBPCFC, once after DBPCFC. FeNO should be done prior to spirometry.
7. On the day of the DBPCFCs, blood draws for exploratory research, including TruCulture, basophil sensitivity, and peripheral blood mononuclear cells (PBMC) samples will be performed before the DBPCFC is performed. On the day of the DBPCFC, titrated SPTs will be performed before the DBPCFC.
8. Samples for PK and ADA analysis should be collected prior to drug administration.
9. Two buccal swabs for genomic analysis can be collected on day 1 or any day after day 1.
10. Only patients who passed a DBPCFC of at least 444 mg (cumulative) at week 24 will undergo a final DBPCFC (up to 2044 mg cumulative).

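### As written, the protocol stops dupilumab permanently for an antihistamine taken within 5 days before the week 4 or week 12 skin prick test, a timing rule that its own schedule treats as test preparation

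*Protocol*

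**What the plan says.** **The stop rule.** Protocol 8.7 gives the consequence of using a prohibited medication: "Their use results in permanent treatment discontinuation but not discontinuation from study". Section 8.3.2.1 lists among the reasons for a permanent stop "Treatment with any prohibited concomitant medication or procedure". Neither section makes an exception. Section 8.3.2.2 adds that "dosing may NOT be resumed if patient met conditions for permanently discontinuing study drug", although that sentence then refers the reader to Section 7.3, which leads to 8.3.2 only by a further cross-reference.

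**The antihistamine item.** The prohibited list in 8.7.1 includes "Treatment with antihistamines within 5 days prior to screening and within 5 days prior to SPTs and day 1 of DBPCFCs". Exclusion criterion 12 in 7.2.2 has almost the same words: "Use of antihistamines within 5 days prior to screening and within 5 days prior to SPTs and day 1 of DBPCFCs". Footnote 3 to the schedule (9.1.1) gives the hold as a plain instruction: "Patients should not take antihistamines within 5 days prior to SPTs and day 1 of the DBPCFCs".

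**When it applies during dosing.** A secondary endpoint in 4.1.2 is "Change from baseline in titrated SPT at week 4, 12, 24, 36 as measured by the average wheal size AUC". Dosing runs from day 1 to week 22, so the week 4 and week 12 tests fall inside it.

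**The SAP.** SAP 4.4 repeats the antihistamine item among prohibited medications but leaves it off the separate list of treatments that require permanent discontinuation. Oral antihistamines given for an allergic reaction are on the list that does not require it.

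**The week 24 challenge after a stop.** Protocol 6.1 says "At week 24, under intensive monitoring, all patients will undergo a DBPCFC up to 2044 mg peanut protein". Section 8.3.2 asks patients who stop drug and stay in the study to keep attending the scheduled visits. The lead-in sentence of 8.3.2.1 concerns study drug dosing only, but its heading also names the food challenge. Section 6.1.3.1 governs both drug and challenge. It lists two or more consecutive missed doses and does not list prohibited medication.

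**The concern.** A medication hold before a skin test protects the reading of that test. The proportionate response to a lapse is to move the test or record a deviation. Here the hold sits in the same list as biologics, live vaccines and allergen immunotherapy, and the whole list carries a permanent stop.

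The situation is foreseeable. Allergic rhinitis and atopic dermatitis are permitted comorbidities (exclusion criterion 3), and Protocol 8.2 expects rescue medication at home after accidental peanut exposure. A child given an oral antihistamine for such a reaction two days before the week 4 visit must stop dupilumab under the protocol. Under SAP 4.4 the same treatment does not require a stop. The SAP does not direct sites, so it shows the inconsistency without curing it.

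The consequence reaches the primary endpoint. A patient stopped early is either challenged long after the last dose or, if a site reads the 8.3.2.1 heading literally, not challenged and counted as a non-responder. Both routes tend to lower the primary proportion. The supportive analysis in SAP 5.6.1 keeps everyone with week 24 challenge data, so it would not separate out patients challenged off drug.

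**Working it through.** **1. The plan's own figures.** Protocol 11.2 assumes 29% on dupilumab against 8%, two-sided 5%, 80% power, normal approximation.

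n = [(1.96 × √(0.08 × 0.92) + 0.8416 × √(0.29 × 0.71)) / (0.29 − 0.08)]² = 18.9, so 19, against the stated 20. Power at 20 is 81.5%. Dropout: 20 / 0.85 = 23.5, so 24. The design reproduces closely, and 29%, 8% and 24 are used below.

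**2. Doses and gaps.** Planned dose days are 1 + 14i for i = 0 to 11, that is days 1, 15, …, 155 (12 doses). The week 24 target day is 169.

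| Stop | Doses given | Doses not given | Last dose | Gap to day 169 |
|---|---|---|---|---|
| None (as planned) | 12 | 0 | day 155 | (169 − 155)/7 = 2 weeks |
| Week 12, visit-day dose given | 7 | 5 | day 85 | (169 − 85)/7 = 12 weeks |
| Week 12, before that dose | 6 | 6 | day 71 | (169 − 71)/7 = 14 weeks |
| Week 4, visit-day dose given | 3 | 9 | day 29 | (169 − 29)/7 = 20 weeks |
| Week 4, before that dose | 2 | 10 | day 15 | (169 − 15)/7 = 22 weeks |

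Protocol 6.1 bases its 12-week follow-up on the time for drug to fall below quantification, so every stopped row is at or beyond that time. The 5-day window before week 24 opens on day 169 − 5 = 164, after the last dose on day 155. There the stop rule has no dosing left to act on.

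**3. Effect on the primary proportion, per affected patient of 24.**

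- Challenged, off-drug response 8% (assumption: the protocol's null rate): (29 − 8)/24 = 0.875 points.
- Challenged, effect fully persists (assumption): (29 − 29)/24 = 0.
- Not challenged, counted as a non-responder: 29/24 = 1.208 points.

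The documents do not say how many patients (k) would be affected, so a range is shown:

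| k | Challenged, 8% off drug | Not challenged |
|---|---|---|
| 0 | 29.0% | 29.0% |
| 1 | 28.1% | 27.8% |
| 2 | 27.3% | 26.6% |
| 3 | 26.4% | 25.4% |

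For k = 2 the expected loss is 2 × 0.21 = 0.42 or 2 × 0.29 = 0.58 responders. For scale, the planned Clopper-Pearson interval at 7 of 24 responders runs from 12.6% to 51.1%.

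**4. Corticosteroid boundary in SAP 4.4 (a separate matter).** The protocol prohibits systemic courses longer than 5 continuous days or 15 days in total. The SAP's discontinuation list uses the same limits, but its non-discontinuation list covers only courses shorter than 5 and 15 days. Exactly 5 or exactly 15 days falls in neither list.

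**The case against.** The strongest reply is that intent is clear. Footnote 3 reads as preparation, SAP 4.4 omits the item from its stop list, and the 8.7.1 wording looks carried over from the exclusion criteria. Protocol 8.7.2 sends questions about permitted drugs to the medical monitor, and SAP 4.4 provides blinded adjudication of rescue treatments. This makes literal enforcement less likely. It does not exempt the item, and adjudication before database lock cannot restore doses already withheld.

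A reader might go further and infer that the protocol leaves open whether a stopped patient has the week 24 challenge. The documents do not support that. Section 8.7 keeps the patient in the study, 8.3.2 asks for the remaining visits, 6.1 has all patients challenged, the 8.3.2.1 lead-in concerns drug only, and 6.1.3.1 does not name prohibited medication. Against this stand the 8.3.2.1 heading and a strained reading in which doses withheld after a mandated stop count as missed. On that reading almost any early stop would cancel the challenge, and the return visits in 8.3.2 would lose their main efficacy assessment.

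Three further inferences also go too far:

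- That 8.3.2.2 directly bars resumption. Its sentence runs through Section 7.3, so the bar is indirect.
- That the loss is unrelated to drug effect. Some antihistamine use could follow reactions on treatment.
- That power is lost. SAP 1.2.3 replaces the test with descriptive statistics, so no decision threshold moves.

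**Conclusion.** The stop rule is a real defect of wording. Followed literally, Protocol 8.7, 8.7.1 and 8.3.2.1 end treatment permanently for a test-timing lapse before the week 4 or week 12 SPT, while footnote 3 and SAP 4.4 point the other way. The week 24 challenge is adequately indicated by the rest of the text, and only the 8.3.2.1 heading is out of line.

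The impact is minor. It is between 0 and about 0.9 points per affected patient of 24 if the challenge is done, and 1.2 points if it is not. This rests on the protocol's 29%, an assumed off-drug response between 8% and 29%, and an unknown number of affected patients. The direction is conservative, and two affected patients shift the estimate by far less than the width of its interval. The change is worth making because following the rule gives a worse result for the patient and for the estimate, and correcting it costs little. The corticosteroid boundary is a small slip that adds nothing to the severity.

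**What to change.** 1. In Protocol 8.7 and 8.3.2.1, exempt antihistamine use inside the 5-day windows from permanent discontinuation: reschedule the SPT or food challenge, or record a deviation, and continue dosing.
2. Delete 'and Food Challenge' from the 8.3.2.1 heading, and state in 6.1.3.1 that doses withheld after a permanent stop do not count as missed.
3. Separately, reword the SAP 4.4 non-discontinuation item for corticosteroids to no more than 5 continuous days and no more than 15 days in total, keeping the 2-day gap before challenges.

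The cost is wording in the next protocol amendment and in the SAP, with no new data. The one practical downside is timing. With a 5-day hold, an antihistamine taken d days before the target day delays the test by 5 − d days. For d = 2 that is 3 days, inside the ±3-day visit window. For d = 1 it is 4 days, one day outside. If the 5 days are counted inclusively, each delay is one day longer. A late SPT recorded under its scheduled visit still counts for that visit, because SAP 6.5 applies no analysis windows to scheduled visits.
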